Percutaneous radiofrequency ablation (RFA) of peripheral cancers is the most studied of the ablative modalities which has been used in medically inoperable patients with small (< 3 cm) peripheral stage I NSCLC (Howington *et al.*, 2013). Although, there is currently no comparative studies, the local control rates seem lower than those reported with SABR or sublobar resection (Howington *et al.*, 2013; Donington *et al.*, 2012). Tumors larger than 3 cm had the highest local recurrence rate (50%) and thus ideal lesions for this treatment should include lesions less than 3 cm in size (Lanuti *et al.*, 2009). Studies show a consistent local control rate of 60%, with a 30% to 40% overall survival at 3 years and a cancer-specific survival of 30% to 40% at 5 years. These

outcomes are better than those seen in untreated patients with clinical stage I NSCLC but worse than those reported with SABR or sublobar resection. In the studies specifically addressing the inoperable stage I NSCLC, the primary tumor relapse rate after percutaneous RFA ranges from 8% to 43% (Donington *et al.*, 2012). The most common reported complications were pneumothorax (18%-62%), pleural effusion (7%-21%), and hemoptysis (4%-11%). Chest tube drainage was required in 5%-25% of subjects. There are also reports of bronchopleural fistula and massive hemoptysis.

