## 1.2. Newly Developed Bronchoscopic Technologies

Newly developed bronchoscopic technologies such as navigational bronchoscopy, including the electromagnetic navigation bronchoscopy (ENB) system, and radial endobronchial ultrasonography (REBUS) have shown that reaching peripheral lung lesions and obtaining diagnosis in humans is both feasible and safe (Eberhardt et al., 2007; Wang Memoli et al., 2012; Brownback et al., 2102; Jensen et al., 2012; Loo et al., 2014; Al-Jaghbeer et al., 2016). In a retrospective chart review of 98 ENB procedures in 92 patients, the diagnostic yield was 60% with a 6% pneumothorax rate (Al-Jaghbeer *et al.*, 2016).

The results of a meta-analysis that included 19 studies totalizing 1,106 patients with peripheral lung nodules reported a total of 40 (6%) pneumothoraces that occurred in 681 procedures, in which two cases were induced using transbronchial biopsy, otherwise, no pneumothorax was ENB procedure-related (Zhang *et al.* 2015). In addition, minor or moderate bleeding was reported in seven cases, and two post-procedure respiratory failure cases were recorded, none of them requiring specific treatment. Other adverse events included two of chest drainage, five of chest pain, three of fever, seven of sore throat, four of hemoptysis, and four of emesis, attributed to sedation or biopsy procedure.

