## 2. STUDY OBJECTIVES

### 2.1. Primary Objective

The primary objective of this study is to assess the safety of photodynamic therapy (PDT) in subjects with solid tumors in peripheral lung prior to surgical resection

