## 10. DATA MANAGEMENT AND STATISTICS

### 10.1. Sample Size/Power Considerations

This study is designed to assess the safety of PDT in subjects with solid lung tumors prior to surgical resection and to assess the lung tumor and healthy tissue response to PDT. The intent of this study is to enroll 10 subjects. This sample size has the following precision for estimation of rates of AE's of special interest (AESI). The following table shows historical AE rates for RFA ranging from <1 to ~50%.

AESI	Rate observed with RFA
Pneumothorax	11-52%
Pleural effusion	6-19%
Hemorrhage	6-18%
Pulmonary artery pseudoaneurysm	0.2%
Needle tract seeding	0.3-0.7%
Cavitation	14%
Bronchopleural fistula	0.6%
Pneumonitis	0.4%

The sample size of N=10 has precision for estimation of AE rates for estimates ranging from <0.01 to ~0.5 as shown in the following list. Precision is measured by 1-sided 95% upper confidence limit (CL) on the estimated AE rate *via* exact binomial distribution. PDT is expected to have lower AE rates than RFA, so, for example, for a RFA historical rate of 0.27 (27%), if no such AE's are observed on PDT, then the TRUE underlying PDT rate is lower than 0.27 with 95% confidence since the upper 95% CL is 0.26 - indicated by "\*" in the list below.

No. of AESIs	Rate	Upper 1-sided 95% confidence limit
0	0.00	0.26*
1	0.10	0.39
2	0.20	0.51
3	0.30	0.61
4	0.40	0.70
5	0.50	0.78

The study will be suspended and re-evaluated from a safety standpoint if 20% of the subjects experience a serious adverse event that is related to PDT.

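### Pneumothorax is set only beside percutaneous RFA rates and gets only upper limits over a period that includes lung resection, so the plan cannot show an excess before surgery

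*Protocol*

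**What the plan says.** Protocol 10.1 states the size, "The intent of this study is to enroll 10 subjects", and how precision is judged: "Precision is measured by 1-sided 95% upper confidence limit (CL) on the estimated AE rate", by the exact binomial method. The only reference rates come from RFA: "The following table shows historical AE rates for RFA ranging from <1 to ~50" percent, with pneumothorax at 11-52%. The section expects PDT to do better and works one example: "PDT is expected to have lower AE rates than RFA, so, for example, for a RFA historical rate of 0.27 (27" percent), "if no such AE's are observed on PDT, then the TRUE underlying PDT rate is lower than 0.27 with 95% confidence". SAP 3.1 repeats the text and both tables.

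The primary objective (Protocol 2.1) is "to assess the safety of photodynamic therapy (PDT) in subjects with solid tumors in peripheral lung prior to surgical resection"; it names no comparator. Section 1.4 presents PDT by navigational bronchoscopy as a possible alternative to RFA and SABR. Section 1.1.1 describes RFA of peripheral cancers as percutaneous. Sections 3.1 and 5.2.1.2 deliver study PDT through a bronchoscope.

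Section 1.2 holds pneumothorax rates for navigational bronchoscopy. A meta-analysis "reported a total of 40 (6%) pneumothoraces that occurred in 681 procedures", and a chart review of 98 procedures gives 6%. The meta-analysis sentence adds that two cases came from transbronchial biopsy and that none was otherwise due to the navigation procedure. Neither Protocol 10.1 nor the SAP uses these rates.

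SAP 5.4.11.1 counts an event as treatment-emergent from the date of injection. It gives each adverse-event percentage a one-sided exact 95% upper limit. It plans no lower limit and no summary restricted to the time before surgery. SAP 2.2 runs the safety evaluation to 90 days after surgery.

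**The concern.** A reader of the final report will want to know whether PDT itself adds pneumothorax. Three features of the plan make that hard to answer.

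- **Reference.** RFA differs from study PDT in both treatment and access route. The protocol itself suggests that route matters: Section 1.3 says the pneumothoraces in the pig study probably came from the chest wall puncture used to place the fibers. A count below the RFA range could therefore reflect the bronchoscope as much as the PDT.
- **Direction.** An upper limit can show that a rate is low. It cannot show that a rate is raised.
- **Window.** Lung resection follows 10 to 15 days after PDT. A rate that pools events before and after it mixes the effects of PDT and of surgery.

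Pneumothorax is where this bites. The Protocol 10.1 example rests on an upper limit of 0.26 for zero events. Among the listed events, only pneumothorax has an RFA range reaching above 0.26; the next highest tops are pleural effusion at 19%, hemorrhage at 18% and cavitation at 14%.

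**Working it through.** **Inputs.** N = 10, one-sided 95% exact limits and RFA pneumothorax 11-52% (Protocol 10.1, SAP 3.1). Diagnostic navigational bronchoscopy: 40/681 = 5.9%, taken as 6% (Section 1.2). Section 1.1.1 quotes a different RFA pneumothorax range, 18-62%; the 10.1 range is used here.

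**1. The plan's own table.** The one-sided 95% upper limit for x events is the 0.95 quantile of Beta(x+1, 10−x). For x = 0 this is 1 − 0.05^(1/10) = 0.259. For x = 0 to 5 the results are 0.259, 0.394, 0.507, 0.607, 0.697 and 0.778. All six agree with the plan's 0.26, 0.39, 0.51, 0.61, 0.70 and 0.78.

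**2. What a zero count says.** If the true rate is 6%, P(0 of 10) = 0.94^10 = 0.539. The worked result, below 27%, would then arise in 54% of such trials with no contribution from PDT in either direction. The upper limit for 0/10 is 0.259/0.06 = 4.3 times 6%, so zero events would not exclude a several-fold excess either.

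**3. What a raised count says.** The one-sided 95% lower limit is the 0.05 quantile of Beta(x, 11−x): 0.037 for 2 events, 0.087 for 3 and 0.150 for 4. Three events is the smallest count whose lower limit exceeds 6%. A rate of 3/10 = 30% lies inside 11-52% but is five times 6%. The planned output would show it only with its upper limit of 0.607.

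**4. How often 3 or more events would occur.** P(X ≥ 3) = 1 − Σ C(10,k) p^k (1−p)^(10−k), summed over k = 0, 1, 2. At p = 0.06: 1 − (0.5386 + 0.3438 + 0.0988) = 0.019.

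| True rate | Multiple of 6% | P(3 or more of 10) |
|---|---|---|
| 6% | 1 | 1.9% |
| 18% | 3 | 26% |
| 24% | 4 | 44% |
| 30% | 5 | 62% |

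**5. If 6% is not the right reference.** The documents give no range for it, so 3% and 10% are assumptions. At 3%, 0/10 has probability 74% and 3 or more 0.3%. At 10%, they are 35% and 7.0%. The lower limit for 3/10 (0.087) is below 10%, so against that reference it would take 4 events.

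**6. Is the narrower window observable?** Yes. Section 5.2.1.3 schedules a chest X-ray before discharge and Section 5.2.2 a chest CT before surgery. The SAP 5.4.11.1 listing carries event start dates.

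**The case against.** The strongest reply is that nothing in the plan is decided against RFA. The rates illustrate precision, and the operative analysis is counts, percentages and upper limits, with no test or threshold. That stands. A reader might infer that the primary safety result is judged against the wrong yardstick, or that a count inside 11-52% would be accepted as normal. The documents set no such rule.

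Second, Section 1.4 makes bronchoscopic delivery part of the procedure under study. If that route causes fewer pneumothoraces than a percutaneous one, the benefit is real. This also stands: RFA is a fair whole-procedure comparator. It simply does not answer how much harm PDT adds.

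Third, the 6% is imperfect. A reader might take it as the rate for bronchoscopy alone. The Section 1.2 qualifier rules that out, and the rate due to navigation alone may be lower. In the other direction, Section 5.2.1.2 places a fiber in the lesion, and possibly several in larger lesions, which may carry its own risk. The 6% can serve only as approximate context.

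A reader might also infer a mismatch in tumor size, because Section 1.1.1 says of RFA "which has been used in medically inoperable patients with small (< 3 cm) peripheral stage I NSCLC" while this study admits tumors under 5 cm. Section 1.3 gives the tumors in RFA studies as 0.7-5.0 cm, so that contrast fails. The point rests on access route.

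Finally, there are safeguards that do not depend on RFA: suspension if 20% of subjects have a PDT-related serious event, a DSMB, and causality assessment for each event. These limit the consequence for subjects. The suspension rule does not cover non-serious pneumothorax, and none of them supplies the missing summary.

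**Conclusion.** The point holds as one of interpretation, mainly of pneumothorax. The RFA contrast cannot separate PDT from access route, and upper limits on events pooled across resection cannot show an excess before surgery. Zero events would be the likeliest result (54%) at a true rate of 6%, while 3/10 would sit inside the RFA range although its lower limit exceeds 6%.

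The gain from correcting this is modest. With ten subjects a threefold excess over 6% yields 3 or more events only 26% of the time, and a fivefold excess 62%. The figures assume ten evaluable subjects and 6% as an approximate reference; at 10%, 3 or more events would arise by chance 7.0% of the time. The documents do not support the stronger conclusion that the safety evaluation as a whole is invalid or that RFA should be dropped.

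**What to change.** 1. **SAP 5.4.11.1:** report pneumothorax with onset from the PDT bronchoscopy to before surgery, among subjects who had that bronchoscopy, with the exact one-sided 95% lower limit beside the upper limit. State the cut-off for anyone who does not reach surgery.
2. **Protocol 10.1 and SAP 3.1:** show the Section 1.2 diagnostic rate (about 6%; 40/681) next to the RFA range as approximate context. Carry over its qualifier on transbronchial biopsy, and note that placing a fiber in the lesion may carry its own risk.
3. **Same sections:** state that a result below RFA reflects access route as well as PDT.
4. **Same table:** keep needle tract seeding as a listed event, but mark its RFA rate as specific to the needle route.

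The cost is some wording, one windowed summary and one extra exact limit. It needs no new visits, imaging or subjects. The downside is an approximate reference that is less favourable to PDT than RFA is.

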### 5.1.3. Enrollment Procedure

Along with the reports confirming the subject's primary diagnosis (Section 4.1), the investigator will check all the eligibility criteria (Section 4.3) of the subject based on all screening procedure results. This requires the availability and evaluation of the results of all screening procedures (Section 5.1.2). The investigator will then submit the Eligibility Verification Form (EVF) to the sponsor's medical monitor to approve the enrollment of the subject. Subjects will be provided with instructions on how to manage light exposure upon enrollment (Study Day 0).

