#### *5.2.1.2. PDT Bronchoscopy (Study Day 3, 40-50 Hours post Photofrin® injection)*

Subjects will return to the institution on Study Day 3 (40-50 hours post Photofrin® injection) for the PDT bronchoscopy procedure. The following assessments will be performed.

1. Vital signs (pulse, blood pressure, temperature, and respiration rate).
2. ECOG Performance Status.
3. Under general anesthesia or deep sedation
  - a. Subjects will undergo a flexible bronchoscopy with navigation guidance to confirm the location and the size of the lesion with the use of radial probe endobronchial ultrasonography (REBUS). This will be captured by video.
  - b. The investigator will select the optical fiber diffuser length to match the tumor length.
  - c. Once the desired placement of the probe is confirmed by REBUS, the investigator will remove the REBUS probe and will insert the selected optical fiber in the lesion under fluoroscopy guidance. This will be captured by video. Exceptionally, the placement of the diffuser adjacent to the tumor for intraluminal activation will be acceptable only if the placement of the optical diffuser in the lesion has been unsuccessful. For larger lesions than 1.5 cm the placement of multiple fibers from different directions will be allowed if feasible.
  - d. After the placement of the optical fiber in the lesion, the 630 nm PDT laser will be turned on and will deliver a light dose of 200 J/cm of diffuser length for an exposure time of 8 minutes and 20 seconds using a pre-set total power output. Subjects presenting multiple metastases, only one lesion would be treated.
4. Re-educate the subject on how to manage light exposure.
5. Record concomitant medications and adverse events.
6. Admit subject for a 48-hour hospitalization period.

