#### *5.2.1.3. Study Day 5 (Hospital Discharge Evaluation)*

Approximately 48 hours after PDT bronchoscopy, the following safety evaluations will be performed to determine if subjects are medically stable to be discharged from the hospital.

1. Vital signs (pulse, blood pressure, temperature, and respiration rate).

2. Clinical labs (Appendix 13-4).
3. Chest X-ray.
4. Record concomitant medications and adverse events.

*5.2.1.3.1. Subject medically stable*

Discharge subject and provide instructions on how to manage light exposure.

*5.2.1.3.2. Subject non-medically stable (Day 6 to Day 10 -Extended hospitalization as required)*

The subject's 48-hour hospitalization can be extended to 72 hours (or longer) at the discretion of the investigator if the subject is deemed medically unstable. During this extended hospitalization, the following assessments should be performed daily until the subject is considered stable and able to be discharged.

1. Vital signs (pulse, blood pressure, temperature, and respiration rate).
2. Record concomitant medications and adverse events.

The day of the discharge, the following assessments should be performed.

1. Clinical labs (Appendix 13-4).
2. Chest X-ray.

The prolongation of hospitalization after 72 hours due to subject being medically unstable is to be reported to the sponsor as a serious adverse event. If a subject is still hospitalized at Day 10, the sponsor should be notified promptly.

*5.2.2. Period II - Surgery (Study Day 13 to Day 18)*

All subjects will undergo surgery as per standard of care 10 to 15 days after PDT. The following assessments will be performed.

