### 8.4.3. Reporting Requirements

#### **8.4.3.1. Serious Adverse Events**

All SAEs, regardless of relationship to study treatment, must be reported by the investigator to the sponsor-designated third party drug safety group (Mapi Group, UK), by completing the SAE form within 24 hours of awareness. This includes SAEs occurring as soon as the subject signs the informed consent (i.e., pre-treatment SAEs). Serious Adverse Events which could be associated with the study procedures and which could modify the conduct of the study are reportable within 24 hours. In addition, any spontaneously reported SAE that occurs within 30 days after the last study procedure for subjects who completed the study protocol or within 90 days after the Photofrin® injection for subjects who prematurely discontinued study treatment should be reported using the SAE form.

The SAE form should be completed as thoroughly as possible, given the information available and time constraints. Upon completion, the SAE form should be signed by the investigator or sub-investigator and faxed or emailed to the designated drug safety group.

Conventional paper-based SAE Form will be provided in the Investigator Study File (ISF). The form will also be electronically available.

Death and surgery should not be reported as an event. Death and surgery are viewed as an outcome of an event, rather than the event itself. In cases where the cause of death is unknown, death may be initially reported as an event. Every attempt should be made to submit a follow-up report identifying the cause of death.

All SAEs will be monitored by Concordia Laboratories Inc. or designee in real time throughout the study.

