#### 8.6. Data Safety Monitoring Board

A Data Safety Monitoring Board (DSMB) will be formed of three experts (two clinicians and one statistician) all of whom are independent of the sponsor and the investigators conducting the study. The DSMB will independently review safety data and, if needed, recommend any changes to the conduct of the study for safety reasons. The DSMB will also review the final analyses.

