#### 8.7. Regulatory Aspects

Concordia Laboratories Inc. has a legal responsibility to notify the Health Products and Food Branch (HPFB) of Canada, the FDA of the USA, European Medicines Agency (EMA), National Competent Authorities and Central Ethics Committees of European Union, and all other foreign regulatory agencies as well as all study sites about the safety of Photofrin®.

The investigator has the responsibility to notify the local Ethics Committee about SAEs. Copies of the notification to the ethics committee must be sent to the sponsor.

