#### 11.8. Protocol Adherence and Investigator Agreement

The investigator must adhere to the protocol as detailed in this document. The investigator will be responsible for enrolling only those subjects who have met protocol eligibility criteria. The investigators will be required to sign an investigator agreement to confirm acceptance and willingness to comply with the study protocol.

At each visit, subjects failing to comply with treatment will be assessed to determine whether the lack of adherence to study treatment is related to safety. The investigator should make every effort to ensure that visits occur at the appropriate intervals. The reason for any deviation in the visit schedule must be documented in the eCRFs.

It is the investigator's responsibility to communicate with their local IRB to ensure accurate and timely information is provided at all phases during the study. The appropriate approvals must be in place prior to recruitment, notification of any SAEs during the study must take place and the IRB must be informed of study completion. The reason for any deviation in the visit schedule must be documented in the eCRFs.

The study will be administered by and monitored by employees or representatives of Concordia Laboratories Inc. The study monitor or Clinical Research Associate (CRA) will visit each site on a periodic basis and perform verification of source documentation for each subject.

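### One PDT-related death may not meet the only stated suspension rule (20% of subjects, no denominator), and neither document requires a pause or prompt DSMB review before the next injection

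*Protocol*

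**What the plan says.** **The rule.** Under Protocol 10.1 the trial is "suspended and re-evaluated from a safety standpoint if 20% of the subjects experience a serious adverse event that is related to PDT". SAP 3.1 repeats the sentence. Neither says whether the 20% is of the 10 planned subjects or of those injected so far, and neither says who re-evaluates. I found no other study-level suspension rule, no spacing between subjects and no hold on injections after a fatal event.

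**What counts.** Under Protocol 8.1, death is one SAE criterion among several. Under 8.4.3.1, "Death and surgery are viewed as an outcome of an event, rather than the event itself", so a fatal event enters the rule as one subject with an SAE. Section 5.2.1.3 adds: "The prolongation of hospitalization after 72 hours due to subject being medically unstable is to be reported to the sponsor as a serious adverse event". Causality is assessed by the investigator (8.4.2).

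**Oversight.**
- Section 8.6: "The DSMB will independently review safety data and, if needed, recommend any changes to the conduct of the study for safety reasons". It gives no meeting schedule and no event that triggers a review.
- Section 8.4.3.1: SAEs go to the sponsor's drug safety group within 24 hours and are monitored by the sponsor in real time. The same limit is set for SAEs that may stem from study procedures and might change how the study is run.
- Section 5.1.3: the investigator sends the eligibility form to the sponsor's "medical monitor to approve the enrollment of the subject".
- Sections 8.7 and 11.8: the sponsor informs regulators and sites. "The investigator has the responsibility to notify the local Ethics Committee about SAEs", and "notification of any SAEs during the study must take place" to the IRB.
- Section 4.7 lists termination by the sponsor among the reasons a subject may leave. Section 11.9 leaves the sponsor and investigator free to act at once for safety.

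**The concern.** Safety is the primary objective of this Phase Ib study. It adds a photosensitizer and a bronchoscopic laser procedure for subjects whose tumor is already judged completely resectable. A rule that counts SAEs without regard to severity can order things the wrong way round: two related hospital stays beyond 72 hours suspend the study, while one related death may not. Someone who follows the written rule exactly could then inject further subjects after a related death with no mandatory halt and no prompt independent review.

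The missing denominator adds to this. Two sites could read the same event differently, and whether a single early SAE suspends the study depends on the reading.

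**Working it through.** **1. The plan's own figures.** The table in 10.1 and SAP 3.1 gives one-sided 95% exact upper limits for 0 to 5 events in 10. The limit for x events is the 95th percentile of Beta(x+1, 10−x): 0.2589, 0.3942, 0.5069, 0.6066, 0.6965, 0.7776. These round to the printed 0.26, 0.39, 0.51, 0.61, 0.70, 0.78. They describe the precision of AE rates. The documents give no operating characteristics for the suspension rule.

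**2. When the rule is met.**

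| Denominator | One subject with a related SAE | Two subjects |
|---|---|---|
| Planned 10 | 1/10 = 10%: not met | 2/10 = 20%: met |
| Injected so far, 1 to 5 | at least 1/5 = 20%: met | met |
| Injected so far, 6 to 10 | at most 1/6 = 16.7%: not met | at least 2/10 = 20%: met |

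This result needs no assumed rate.

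**3. How often the gap could matter (illustration).** The documents give no related-death rate. The 9-subject peripheral PDT series in Protocol 1.3 mentions two pneumothoraces and no death. Read as 0/9, its one-sided 95% upper limit is 1 − 0.05^(1/9) = 28.3%, so it does not settle the rate.

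Assume 10 subjects injected in order, each outcome known before the next injection. Let p be the related-death rate, q the nonfatal related SAE rate and r = 1 − p − q. The event of interest is that the first related SAE is a death in subject k, the rule is unmet at k, and k ≤ 9 so that subjects remain.

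- Fixed 10: p × Σ(k=1..9) r^(k−1) = p(1 − r^9)/(1 − r)
- Running count: only k = 6 to 9 qualify, giving p × r^5(1 − r^4)/(1 − r)

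| p | q | r | Fixed 10 | Running count |
|---|---|---|---|---|
| 1% | 10% | 0.89 | 5.9% | 1.9% |
| 2% | 10% | 0.88 | 11.4% | 3.5% |
| 1% | 20% | 0.79 | 4.2% | 0.9% |
| 2% | 20% | 0.78 | 8.1% | 1.7% |

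First row, fixed: 0.01 × (1 − 0.3504)/0.11 = 0.0591.

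**4. Further exposure if it happens.** The mean number of further subjects the rule would allow, until a second related SAE or subject 10, is 3.47 to 4.24 (fixed) or 2.19 to 2.35 (running) across these four rows.

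**5. A limit of the running figures.** They assume outcomes are known before the next injection. With about five sites and follow-up to 90 days after surgery, a death in subject 4 that is learned of after six injections would be 1/6 and would also miss the rule.

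**6. How often a single-event trigger would pause the study.** If s is the rate of fatal or life-threatening related SAEs, the chance of at least one such event while subjects remain is 1 − (1 − s)^9. This gives 8.6% at s = 1% and 16.6% at s = 2%. Since s includes deaths, it is at least p, so this grid should not be compared row for row with step 3.

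**The case against.** The strongest reply is that the 20% rule is not the only route to action. The DSMB can recommend changes at any time, and SAEs reach the sponsor's safety group within 24 hours. Section 8.4.3.1 itself contemplates that one procedure-related SAE may alter the study, and the sponsor and investigator may act at once. Porfimer PDT is already approved for endobronchial NSCLC, there is one fixed dose with no escalation, and about 10 subjects over 9 months is roughly one a month. That usually leaves time to review a death before the next injection. A DSMB operating document, which neither text cites, may also hold an ad hoc trigger.

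Much of this stands. A reader might infer that the study would carry on after a death, or that nothing below 20% can stop it. The documents do not support either: a voluntary pause is likely. What remains is that each safeguard permits a pause and none requires one. The medical monitor's approval is tied to eligibility, and notifying regulators and ethics committees is not a hold.

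The illustration is also open to challenge. It measures the rule followed literally, with nobody using their discretion, so it is not a forecast of harm. Death rates of 5-10% would give much larger figures, but nothing in the documents points to them, and they are left out. The result depends heavily on which denominator is meant, which is itself part of the point.

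**Conclusion.** The point holds as a gap in what is mandatory. The written rule can suspend for two nonfatal related SAEs and not for one related death, and no text requires a halt or DSMB review before the next injection. That conclusion rests only on the wording and the fractions in step 2.

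Its size, 4.2-11.4% or 0.9-3.5% depending on the denominator, rests on assumed rates, sequential injection with known outcomes, and literal use of the rule. It would be inaccurate to say that a single death never triggers suspension: on a running count, a lone event among the first five does. The claim is also limited to the protocol and SAP. This is a change the sponsor should make, because it is cheap and protects subjects. It does not show that the study lacks safety oversight.

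**What to change.** 1. **Single-event trigger (Protocol 8.6 and 10.1).** Any single fatal or life-threatening SAE rated *Reasonable Possibility* suspends further enrollment and injection until the existing DSMB completes an ad hoc review.
2. **Subjects between injection and light.** "Subjects will return to the institution on Study Day 3", 40-50 hours after injection, so a halt may catch someone already photosensitized. For that subject the medical monitor and the investigator decide, and document, whether to give light.
3. **Denominator.** Keep the 20% rule and define it on subjects injected so far, so that one related SAE among the first 5, or two at any time, suspends. Writing only *two or more* would loosen the rule on the running reading: at an assumed 10% or 20% nonfatal related SAE rate, at least one occurs in the first five with probability 1 − 0.9^5 = 41% or 1 − 0.8^5 = 67%. If the sponsor intends 2 of the planned 10, the text should say so.
4. **Responsibility.** Name the DSMB as the body that re-evaluates under either trigger, and align SAP 3.1.

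**Cost.** A short amendment with the review that 11.9 requires for safety changes, using a board already planned. No subjects, visits or data are added. The new trigger may cause a brief pause, with the 8.6-16.6% chance from step 6 at s = 1-2%. If the planned 10 was intended, moving to a running count also suspends more often: 45.8% against 26.4% at an assumed total related-SAE rate of 10%, and 75.8% against 62.4% at 20%.
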